Amendment 1 (v2.0)	20NOV2019	

• Editorial changes were made throughout the document to improve overall clarity

• Updated list of sections/sub-sections/appendices (including removal of sections/sub-sections/appendices which were not applicable in this study)

• List of abbreviations updated to include all abbreviations used in this document

• Added the secondary estimand definition, in section 2.1

• Specified the statistical hypotheses to be tested, in section 2.2

• Updated section 3 to align with the protocol amendment 2, dated 04 September 2019

• Updated section 4.2 to include additional subgroups

• Updated section 5 to include all the definitions used in the document and align with the existing definitions with the latest available DES

• Updated “Actual treatment received” definition to capture all the scenarios, in section 5.1

• Expanded the definitions of primary/secondary/exploratory endpoints, in section 5.4, section 5.5 and section 5.6

• Defined separate analysis sets for Part A and Part B, in section 6.1 and section 6.2

• Expanded on the details of primary, secondary and exploratory analysis, in section 9.5

• Section 9.6 updated to specify the details of safety analyses

• Updated section 10 to clarify that there are no changes to the protocol specified analyses

Version Number	Date (DDMMYYYY)	Summary of Changes, including rationale for changes
Amendment 2 (v3.0)	04JUN2020	
 
• Editorial changes were made throughout the document to improve overall clarity due to changes in SAP amid COVID19 pandemic
 
• List of abbreviations updated to include all abbreviations used in this document
 
• Updated section 4.2 to clarify regions and subgroups for S. aureus and absolute eosinophil
 
• Updated section 5.1 to clarify definition of actual treatment, TEAE and DRE
 
• Updated section 5.3 to clarify baseline IGA, baseline EASI, improvement from baseline and duration of AD
 
• Updated section 5.4 to modify content pertaining to IGA, EQ-5D-3L, POEM, PGI-S, Pruritus NRS, DLQI and SCORAD
 
• Updated section 6.6 to add clarification on definition of mFAS
 
• Updated section 8.3.2 to clarify descriptive summaries and imputation of missing data for secondary and exploratory endpoints along with missing dates needed to calculate duration of AD
 
• Updated section 9.4 to clarify regions pertaining to demographic information and summary of baseline disease characteristics
 
• Updated section 9.5 to clarify the analysis set to be used for efficacy analyses and statistical tests
 
• Updated section 9.5.2 to clarify covariates of MMRM model for SCORAD and Pruritus NRS at week 16 analysis along with censoring of subjects pertaining to time to achieving EASI 50/75/90 response prior to switching
 
• Updated section 9.5.3.1 to clarify exploratory endpoint summarization and to clarify covariates for MMRM modeling for continuous endpoints, change from baseline in each of IGA, EASI, SCORAD, Pruritus NRS, PGI-S, POEM and DLQI at week 24, week 36 and week 52 and also for change from switching date for part A. Updated part B to clarify censoring for subjects pertaining to time to achieving EASI 50/75/90 response
 
• Updated section 9.6 to clarify two different periods of safety analyses for Part A
 
• Updated section 9.6.1 to clarify summarization of adverse events, MedDRA query to be used for Guillain Barre Syndrome, to clarify EOI for 'severe infection' identification and exposure-adjusted event rate and exposure adjusted incidence rate for final analysis
 
• Updated section 10 to clarify changes from protocol-specified analyses
 
• Updated section 13 to modify analysis window for vitals of week 16 and added analysis window for S. aureus
 

## List of Abbreviations and Definition of Terms

Abbreviation or Term	Definition/Explanation
AD	Atopic Dermatitis
AE	Adverse Event
CI	Confidence Interval
CRF	Case Report Form
CTCAE	Common Terminology Criteria Adverse Events
DLQI	Dermatology Life Quality Index
EASI	Eczema Area and Severity Index
EASI 50	50% reduction from baseline in EASI score
EASI 75	75% reduction from baseline in EASI score
EASI 90	90% reduction from baseline in EASI score
ECG	Electrocardiogram
EQ-5D-3L	EuroQOL quality of life 5-dimensions 3-level version
EQ VAS	EuroQOL Visual Analog Scale
HRQoL	Health Related Quality of Life
Ig	Immunoglobulin
IGA	Investigator's Global Assessment
IGA 0/1	response of 0 (clear) or 1 (almost clear) skin on IGA scale
IP	Investigational Product
NRS	Numerical Rating Scale
PD	Pharmacodynamics
PGI-S	Patient Global Impression of Severity
PK	Pharmacokinetics
PRO	Patient-Reported Outcome
POEM	Patient Oriented Eczema Measure
QOL	Quality Of Life
Q2W	every 2 weeks
Q4W	every 4 weeks
SAE	Serious Adverse Event
SAP	Statistical Analysis Plan
SC	Subcutaneous
SCORAD	Scoring of Atopic Dermatitis
TCS	Topical Corticosteroid
TCI	Topical Calcineurin Inhibitors
TEAE	Treatment-Emergent Adverse Event
TSLP	Thymic Stromal Lymphopoietin
TTO	Time trade-off

## 1. Introduction

The purpose of this Statistical Analysis Plan (SAP) is to provide details of the statistical analyses that have been outlined within the protocol for study 20170755, AMG 157 dated **04 September 2019**. The scope of this plan includes two interim analyses that will be performed by an independent statistician, the primary analysis and the final analysis, that are planned and will be executed by the Amgen Global Biostatistical Science department unless otherwise specified.

## 2. Objectives, Endpoints and Hypotheses

### 2.1 Objectives and Endpoints

Objectives	Endpoints
Primary – Part A	

To evaluate the effect of tezepelumab compared with placebo, assessed using the Investigator's Global Assessment (IGA) and Eczema Area and Severity Index (EASI)

	

IGA score of 0 (clear) or 1 (almost clear) (IGA 0/1) at week 16

75% reduction in EASI (EASI 75) at week 16

The first primary estimand consists of:

- Target population – patients with moderate-to-severe atopic dermatitis (**AD**).
- Endpoint – IGA 0/1 at week 16.
- Intercurrent event – there are 2 intercurrent events, discontinuation of IP before week 16 and **concurrent use** of rescue medication **with TCS/TCI** between day **29** and week 16. Treatment effects will be estimated for subjects regardless of whether patients complete 16 weeks of **study treatment**. The use of rescue medication is captured through the endpoint definition in **Section 5.5, and use of TCS/TCI will be classed as a non-response**.
- Summary measure – odds ratio comparing the odds of achieving endpoint on tezepelumab 420 mg Q2W compared to the odds of achieving endpoint on placebo.

In summary, the first primary estimand is the odds ratio between tezepelumab 420 mg Q2W and placebo in achieving IGA 0/1 at week 16, in the absence of rescue medication with **TCS/TCI regardless of whether patients complete 16 weeks of study treatment**, in patients with moderate-to-severe AD.

The second primary estimand is the odds ratio between tezepelumab 280 mg Q2W and placebo in achieving IGA 0/1 at week 16, in the absence of rescue medication with **TCS/TCI regardless of whether patients complete 16 weeks of study treatment**, in patients with moderate-to-severe AD.

The third primary estimand is the odds ratio between tezepelumab 420 mg Q2W and placebo in achieving EASI 75 at week 16, in the absence of rescue medication with **TCS/TCI regardless of whether patients complete 16 weeks of study treatment**, in patients with moderate-to-severe AD.

The fourth primary estimand is the odds ratio between tezepelumab 280 mg Q2W and placebo in achieving EASI 75 at week 16, in the absence of rescue medication with **TCS/TCI regardless of whether patients complete 16 weeks of study treatment**, in patients with moderate-to-severe AD.

Secondary – Part A	


To estimate the effect of tezepelumab compared with placebo on the efficacy measure of EASI

	

50% and 90% reduction in EASI (EASI 50/90) at week 16

To estimate the time needed to reach EASI 50/75/90

	

Time at which EASI 50/75/90 is achieved from day 1

To estimate the effect of tezepelumab compared with placebo on the efficacy measure of Scoring Atopic Dermatitis (SCORAD)

	

SCORAD at week 16

To estimate the effect of tezepelumab compared with placebo on the patient-reported outcome (PRO) measure of pruritus assessed using a numeric rating scale (NRS)

	

Pruritus NRS at week 16

To characterize the pharmacokinetics (PK) of tezepelumab

	

Serum trough concentrations of tezepelumab at scheduled visits

The secondary estimands are described in the same way as primary estimands except the endpoint attribute will change for EASI 50/90 at week 16, SCORAD at week 16 and Pruritus NRS at week 16, where the summary measure changes to be the Least Square Mean difference; and time at which EASI 50/75/90 is achieved from day 1, where the summary measure changes to be the median time to achieve EASI 50/75/90 from day 1.

Safety – Part A and Part B	

 
To establish the safety and tolerability of tezepelumab compared with placebo
 
	
 
Subject incidence of adverse events (including serious adverse events)
 

Exploratory – Part A and Part B	

 
To estimate the long-term effect of tezepelumab on the efficacy measures of EASI, SCORAD, and Pruritus NRS
 
	
 
IGA 0/1 at week 24, week 36, and week 52
 
EASI 75 at week 24, week 36, and week 52
 
EASI 50/90 at week 24, week 36, and week 52
 
SCORAD at week 24, week 36, and week 52
 
Pruritus NRS at week 24, week 36, and week 52
 


 
To investigate potential biomarker development by biochemical analysis of blood or skin samples
 
	
 
Serum biomarkers may include but are not limited to IgE, CCL17, and CCL22
 
RNA transcriptional changes in blood and lesional versus non lesional skin
 

 
To explore the effect of tezepelumab on Patient Global Impression of Severity (PGI-S)
 
	
 
Change from baseline in PGI-S at scheduled visits
 

 
To evaluate the effect of tezepelumab on health-related quality of life (HRQoL) assessed using the Dermatology Life Quality Index (DLQI)
 
	
 
Change from baseline in DLQI at scheduled visits
 

 
To explore the effect of tezepelumab on POEM
 
	
 
Change from baseline in POEM at scheduled visits
 

 
To explore the effect of tezepelumab on EQ-5D-3L
 
	
 
Change from baseline in EQ-5D-3L at scheduled visits
 

 
To evaluate the immunogenicity of tezepelumab
 
	
 
Anti-tezepelumab antibodies
 

 
To investigate the effects of drug target genes and AD genes and/or subject response to tezepelumab
 
	
 
Gene polymorphisms that may influence clinical response to study drug, such as filaggrin and TSLP
 

Exploratory – Part B	

To evaluate the effect of tezepelumab compared with placebo, assessed using the IGA and EASI

	

IGA score of 0 (clear) or 1 (almost clear) (IGA 0/1) at week 16

EASI 75 at week 16

To estimate the effect of tezepelumab compared with placebo on the efficacy measure of EASI

	

EASI 50/90 at week 16

To estimate the time needed to reach EASI 50/75/90

	

Time at which EASI 50/75/90 is achieved from day 1



To estimate the effect of tezepelumab compared with placebo on the efficacy measure of SCORAD

	

SCORAD at week 16

To estimate the effect of tezepelumab compared with placebo on the PRO measure of pruritus assessed using an NRS

	

Pruritus NRS at week 16

To characterize the PK of tezepelumab

	

Serum trough concentrations of tezepelumab at scheduled visits

To establish the safety and tolerability of tezepelumab compared with placebo

	

Subject incidence of adverse events (including serious adverse events)

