2.2 Schedule of Activities

Table 2-1. Schedule of Activities for Part A and Part B (Screening Through Week 24)

	Screening ^a (up to -28 d + 7 d)	Treatment Period (52 weeks) ^{b, p}													
		Day 1	Wk 2	Wk 4	Wk 6	Wk 8	Wk 10	Wk 12	Wk 14	Wk 16	Wk 18	Wk 20	Wk 22	Wk 24	
GENERAL AND SAFETY ASSESSMENTS															
Informed consent	X														
Informed consent for optional biomarker/pharmacogenetic assessments	X														
Verify eligibility criteria	X	X ^o													
Demographics	X														
Physical examination	X														
Physical measurements	X														
Medical and dermatology history	X														
Randomization		X													
Substance use	X														
12-lead ECG ^c	X														
Vital signs ^d	X	X	X	X	X	X	X	X	X	X	X	X	X	X	X
Adverse events		X	X	X	X	X	X	X	X	X	X	X	X	X	X
Serious adverse events	X	X	X	X	X	X	X	X	X	X	X	X	X	X	X
Disease-related events	X	X	X	X	X	X	X	X	X	X	X	X	X	X	X
Concomitant therapies review		X	X	X	X	X	X	X	X	X	X	X	X	X	X
LABORATORY ASSESSMENTS															
Serum or urine pregnancy test ^e	X	X		X		X		X		X		X		X	
Coagulation	X	X							X						
Hematology	X	X						X							X
Chemistry	X	X						X							X
HIV, Hepatitis B and C screening	X														
Urinalysis (dipstick)	X	X						X							X
Anti-tezepelumab-antibody		X						X							X
Serum immunoglobulins ^f	X	X								X					

Footnotes defined on last page of the table

Table 2-1. Schedule of Activities for Part A and Part B (Screening Through Week 24)

	Screening ^a (up to -28 d + 7 d)	Treatment Period (52 weeks) ^{b, p}													
		Day 1	Wk 2	Wk 4	Wk 6	Wk 8	Wk 10	Wk 12	Wk 14	Wk 16	Wk 18	Wk 20	Wk 22	Wk 24	
PPD or Quantiferon GOLD	X														
STUDY-SPECIFIC ASSESSMENTS															
eDiary device distribution and training	X														
Electronic diary ⁹	Completed in the morning at home on eDiary														
Assessment of EASI and IGA	X	X		X	X	X	X	X		X				X	
SCORAD		X		X		X		X		X				X	
EQ-5D-3L, POEM, DLQI, PGI-S		X		X		X		X		X				X	
Tracking of TCS use (Part B subjects only)	X	X	X	X	X	X	X	X	X	X	X	X	X	X	
PHARMACOKINETIC ASSESSMENTS															
PK sampling ^k		X	X ⁱ	X ⁱ				X		X				X ⁱ	
PHARMACOGENETIC ASSESSMENTS															
Sample for DNA analysis (optional)		X													
STUDY TREATMENT															
Administration of tezepelumab or placebo ^m		X ⁿ	X	X	X	X	X	X	X	X	X	X	X	X	

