### 3.2 Sample Size

In Part A of this study, a total of 240 subjects will be randomized in a 1:1:1:1 ratio to tezepelumab 420 mg SC Q2W, 280 mg SC Q2W, 210 mg SC Q4W, and placebo (approximately 60 in each group). There is at least 85% power for each co-primary endpoint, assuming IGA 0/1 response rates of 10% and 40% for placebo and the highest tezepelumab dose group (420 mg SC Q2W), respectively, and assuming EASI response rates of 15% and 50%, respectively. These assumed treatment effects are based on results of other new agents (**recent biologic treatment**) in this indication ([\(DUPIXENT, 2017\)](#)). These calculations used a 2-sided  $\chi^2$  test at a significance level of 0.025 (to reflect the Bonferroni-based gatekeeping procedure described in [Section 9.5.1](#)) and assumed a 10% dropout rate.

Part B of this study is exploratory. A sample size of 60 subjects (40 in the tezepelumab 420 mg SC Q2W group and 20 in the placebo group) was chosen as an adequate sample size to provide initial evidence of tezepelumab as a promising agent for adjunct therapy. **The sample size of 60 in Part B was based on practical considerations rather than statistical considerations. For example, to observe treatment effect differences of tezepelumab 420 Q2W vs. placebo as 30% for IGA 0/1 and 35% for EASI 75 at week 16, the half-width of 95% CI will be approximately 20%.**

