**Target Treatment Effect (TTE)**

A Target Treatment Effect (TTE) for IGA 0/1 is based on an odds ratio equivalent to or greater than 5.29 comparing tezepelumab to placebo. The odds ratio of 5.29 is determined by the following assumption: tezepelumab response rate is 37% and placebo rate is 10% (Simpson et al, 2016). The observed placebo rate may be

different from the assumed 10%, therefore, the target tezepelumab response rate may be adjusted fixing the odds ratio at 5.29.

A Target Treatment Effect (TTE) for EASI 75 is based on an odds ratio equivalent to or greater than 5.67 comparing tezepelumab to placebo. The odds ratio of 5.67 is determined by the following assumption: tezepelumab response rate is 50% and placebo rate is 15% ([Simpson et al., 2016](#)). The observed placebo rate may be different from the assumed 15%, therefore, the target tezepelumab response rate may be adjusted fixing the odds ratio at 5.67.

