#### 9.5.2 Analyses of Secondary Efficacy Endpoint(s)

The secondary estimands will be analyzed using **FAS – Part A**. Secondary endpoints are defined in [Section 5.6](#).

For the binary endpoint, EASI 50/90 at week 16, the treatment effect will be **analyzed** using a logistic regression model adjusting for baseline EASI. From this model, odds ratio and 95% CIs will be reported comparing each tezepelumab dose group to placebo.

The time to achieving EASI 50/75/90 response prior to switching to tezepelumab 420 mg Q2W will be summarized by Kaplan-Meier (KM) curves, the number of subjects achieving EASI 50/75/90 and the number of subjects censored will be provided at available time points. Subjects who do not achieve EASI 50/75/90 will be censored at the date when formal assessments of non-responder (as defined in protocol, that is, not achieve at least 50% improvement in EASI at week 16

compared to baseline) are recorded or end of study date, whichever is the earliest. Subjects who receive rescue medication from day 29 will be censored at the point when subjects receive rescue medication.

The treatment effect for change from baseline in SCORAD and Pruritus NRS each at week 16 will be analyzed using a **Mixed Model for Repeated Measures (MMRM)**. The model for change from baseline in SCORAD at week 16 will include visit and baseline SCORAD as covariates and an interaction term between arm and visit. The model for change from baseline in Pruritus NRS at week 16 will include visit and baseline Pruritus NRS as covariates and an interaction term between arm and visit. **AR(1) variance-covariance structure will be used.** Least square means and corresponding 95% CI will be calculated for each treatment group and for the difference between treatment groups.

Serum concentration will be summarized descriptively by treatment group for each sampling time point using the PK analysis set.

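### The SAP summarises time to EASI 50/75/90 by a median that, at the plan's own 15% placebo rate, placebo is not expected to reach by week 16 for EASI 75 or EASI 90, and SAP 9.5.2 does not report a median

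*SAP*

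**What the plan says.** SAP 2.1 defines the secondary estimands like the primary ones, which compare a tezepelumab dose with placebo, and changes the endpoint and the summary measure. For time to EASI response the estimand is one "where the summary measure changes to be the median time to achieve EASI 50/75/90 from day 1".

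SAP 3.2 has "approximately 60 in each group" and plans power "assuming EASI response rates of 15% and 50%, respectively" (placebo, then 420 mg Q2W), with 10% dropout. The Target Treatment Effect paragraph in SAP 5.4 repeats the 15% and 50% as EASI 75 rates. Neither document gives a planning rate for EASI 50 or EASI 90, or any rate for 280 mg or 210 mg.

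SAP 9.5.2 plans Kaplan-Meier curves up to the switch to 420 mg, where "the number of subjects achieving EASI 50/75/90 and the number of subjects censored will be provided at available time points". Subjects who do not achieve the threshold are censored at the week-16 assessment that classes them as EASI 50 non-responders or at end of study, whichever comes first. Subjects rescued from day 29 are censored at rescue. No median, confidence interval or between-arm contrast is named, and nothing is said about a median that is not reached.

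In Protocol Table 2-1 the row "Assessment of EASI and IGA" has post-baseline visits at weeks 4, 6, 8, 10, 12, 16 and 24. Later EASI visits follow to week 52 and week 70 (SAP Appendix A). SAP 7.2 limits the primary analysis to data through week 16.

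**The concern.** A Kaplan-Meier median exists only once the curve falls to one half. The objective is to estimate how long it takes to reach each EASI threshold, and the SAP commits to the median as the number that answers it. If the planning rates are right, the placebo arm has no such number for EASI 75 or EASI 90 at the week-16 analysis, and the 420 mg arm may or may not have one for EASI 75.

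Follow-up after week 16 does not cure this. Under the Part A switching rule, EASI 50 non-responders leave their randomised regimen, and 9.5.2 censors them at the week-16 assessment. Only the EASI 50 responders who have not yet reached the higher threshold remain at risk. The curve then treats the removed subjects, and those censored at rescue, as if they had the same prospects as the ones who remain. They are the subjects doing worst. A placebo median produced this way could be misleading, whereas a median reported as not reached is at least honest.

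The estimand section also names a quantity that the analysis section does not list, so two programmers could produce different tables.

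**Working it through.** **Inputs.** n = 60 per arm, 10% dropout (54 evaluable), EASI 75 rates 0.15 and 0.50, IGA 0/1 rates 0.10 and 0.40, two-sided alpha 0.025 (all SAP 3.2). Censoring rule from SAP 9.5.2.

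**1. The plan's own figure.** SAP 3.2 claims at least 85% power for each co-primary endpoint. With the pooled chi-square approximation, power = Φ((|p2 − p1| − z·s0)/s1), where z = 2.2414, s0 = √(2p̄(1 − p̄)/n) and s1 = √((p1(1 − p1) + p2(1 − p2))/n).
- EASI 75, n = 54: p̄ = 0.325, s0 = 0.0901, s1 = 0.0836. (0.35 − 0.2020)/0.0836 = 1.77, so power is 96.2%.
- IGA 0/1, n = 54: p̄ = 0.25, s0 = 0.0833, s1 = 0.0782. (0.30 − 0.1868)/0.0782 = 1.45, so power is 92.6%.

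Both exceed 85%, so the power statement holds. The EASI 75 odds ratio of 5.67 also reproduces: (0.50/0.50)/(0.15/0.85) = 5.67.

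**2. Placebo, EASI 75, by week 16.** Expected events are 60 × 0.15 = 9 (54 × 0.15 = 8.1). Without earlier censoring, a median needs 30 of 60 (27 of 54). The 15% is response at week 16, while the curve counts first achievement at any visit, so the relevant rate p may be higher. P(X ≥ 30) for X ~ Binomial(60, p):

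| Ever-response p | Expected events | P(at least 30) |
|---|---|---|
| 0.15 | 9 | 2.1e-10 |
| 0.20 | 12 | 2.1e-7 |
| 0.30 | 18 | 0.0009 |
| 0.35 | 21 | 0.012 |
| 0.40 | 24 | 0.075 |

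With n = 54 and 27 needed, p = 0.15 gives 1.7e-9 and p = 0.35 gives 0.017. A larger trial would not help: at 15% the population curve at week 16 stands at 0.85. Every EASI 90 responder is also an EASI 75 responder, so the placebo EASI 90 count is no higher.

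**3. Could censoring at rescue bring the placebo curve down?** Keep the 9 events and suppose a fraction r of the arm is censored before any event, the extreme case. Then S(16) = 1 − 9/(60(1 − r)):
- r = 0.3: 1 − 9/42 = 0.79
- r = 0.5: 1 − 9/30 = 0.70
- r = 0.7: 1 − 9/18 = 0.50

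It would take 70%.

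**4. 420 mg, EASI 75, by week 16.** P(X ≥ 30 of 60) is 0.55 at p = 0.50, 0.82 at 0.55 and 0.96 at 0.60.

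**5. Placebo after week 16.** With S(16) = 0.85, the curve reaches 0.50 if a fraction c of those still at risk later convert, where c = 1 − 0.50/0.85 = 0.41. To see how few subjects this involves, the 9.5.2 rule was simulated (1,000 trials per setting) under assumptions that are not in the documents: 15% achieve EASI 75 by week 16, 20% of the remaining unrescued subjects are EASI 50 responders, and 20%, 40% or 60% of those later reach EASI 75 at weeks 24 to 52.

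| Rescued among non-achievers | Still at risk after week 16 | Late events (c = 20/40/60%) | Trials with a placebo median |
|---|---|---|---|
| None | about 10 of 60 | about 2 / 4 / 6 | 7% / 47% / 89% |
| 30% | about 7 of 60 | about 1 / 3 / 4 | 12% / 48% / 84% |

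In all six settings no median fell at or before week 16. Whether a median exists depends on a handful of late events in selected subjects.

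**The case against.** The strongest reply has four parts.

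First, follow-up does not end at week 16 for everyone. Week-16 EASI 50 responders stay on randomised treatment to week 52 and at risk to end of study. This stands. A reader might infer that the placebo median can never exist, that any median must fall at weeks 4 to 16, or that the problem is the same under every censoring rule. The documents support none of these. The censoring rule decides whether a late median appears. The point is limited to what is reached by week 16 and to what a later median would mean.

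Second, the binomial figures are not the Kaplan-Meier estimator. This stands for 420 mg. A reader might cut the 50% to 45% for dropout and quote a probability of 0.26, but 9.5.2 censors dropouts who have not achieved the threshold and does not count them as failures. Since 50% is a week-16 rate and the curve counts first achievement at any visit, 0.55 is the low end. For placebo the conclusion survives both corrections (steps 2 and 3).

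Third, the objective for this endpoint does not mention placebo, and 9.5.2 schedules no contrast of medians. This is fair, although 2.1 carries over the dose-versus-placebo form of the primary estimands. Even if only per-arm medians are meant, placebo would have none by week 16.

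Fourth, curves, counts and week-16 EASI 50/90 odds ratios are already planned, EASI 75 by visit is summarised descriptively, and a median that is not reached is an interpretable result. True. What is missing is a stated summary that can be estimated in each arm, its difference from placebo by visit with an interval, and a rule for a median that is not reached.

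**Conclusion.** The point holds in limited form. At the plan's own 15%, the placebo median for EASI 75, and therefore for EASI 90, is not expected by week 16: 9 events of 60 against 30 needed, with probability about 2e-10, and 0.012 even at 35% ever-response. At 420 mg the EASI 75 median is reached by week 16 with probability about 0.55 to 0.96 for ever-response of 50% to 60%. A placebo median that appears later would rest on a few selected responders and would not describe the randomised arm. SAP 9.5.2 does not deliver the summary that 2.1 names.

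This rests on the SAP 3.2 rates, 60 per arm, and 9.5.2 as written. The late-median percentages rest on assumed conversion and rescue rates and show fragility only. No figures are claimed for EASI 50, for 280 mg or for 210 mg, because the documents give no rates. EASI 90 follows only as a bound from EASI 75. A reader might infer that a confirmatory result is at risk. It is not: secondary analyses are descriptive (Protocol 10.3.2.2, SAP 9.5), and alpha, sample size and the primary tests are untouched. This is an inexpensive improvement worth making.

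**What to change.** - **SAP 2.1:** replace the median with the cumulative proportion of subjects who have achieved EASI 50, 75 and 90 by weeks 4, 6, 8, 10, 12 and 16.
- **SAP 9.5.2:** report these proportions for each arm, and the difference of each tezepelumab dose from placebo, with 95% CIs. Count TCS/TCI rescue from day 29, or missing data, occurring before first achievement as non-achievement. This matches how SAP 2.1, 5.5 and 9.5.1.1 treat rescue and missing data for the primary endpoints.
- **Median:** report it only where it is reached by week 16, and otherwise state that it was not reached. The Kaplan-Meier curves can stay as a descriptive display.

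The cost is a few sentences in two SAP sections and one extra table from data already collected. The downside is that the headline becomes a proportion by visit and not a single time, which is a little less direct to quote.
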